6.4.2 Withdrawal from Study

Subjects who wish to withdraw from the study will be invited to return, if willing, for a single additional EDV, unless all study procedures to be completed at the EDV had been completed within the past 30 days.

6.4.3 Subjects Lost to Follow-up

For subjects who are lost to follow-up (ie, those subjects whose status is unclear because they fail to appear for study visits without stating an intention to withdraw), the Investigator should show due diligence by documenting in the source documents the steps taken to contact the subject, eg, dates of telephone calls, registered letters, etc.

Efforts to ensure complete subject follow-up include proactive site contact of subjects who have missed visits (at least 3 documented attempts to reach by telephone and at least 3 documented attempts to reach by letter) or through emergency/other contact if subjects have provided such contacts. Email can be used for contact and scheduling of visits as long as subjects have given permission for email contact.

6.5 Study Suspension or Termination

The Sponsor reserves the right to temporarily suspend or terminate this study at any time. The reasons for temporary suspension or termination of the study may include, but are not limited to, the following:

- The incidence or severity of AEs indicates a potential health hazard to subjects.
- Subject enrollment is unsatisfactory.

- Noncompliance that might significantly jeopardize the validity or integrity of the study.
- Sponsor decision to terminate development.

If Sponsor determines that temporary suspension or termination of the study is required, Sponsor will communicate the reasons for taking such action to all participating investigators (or head of the medical institution, where applicable). When feasible, Sponsor will provide advance notice to all participating investigators (or head of the medical institution, where applicable) of the impending action.

If the study is suspended or terminated for safety reasons, Sponsor will promptly inform all Investigators, heads of the medical institutions (where applicable), and/or institutions conducting the study. Sponsor or designee will also promptly inform the relevant regulatory authorities of the suspension/termination along with the reasons for such action. Where required by applicable regulations, the Investigator or head of the medical institution must inform the IRB/IEC promptly and provide the reason(s) for the suspension/termination. If the study is suspended for safety reasons and it is deemed appropriate by the Sponsor to resume the study, approval from the relevant regulatory authorities (and IRBs/IECs, when applicable) will be obtained prior to resuming the study.

6.6 End of Study

The primary analysis of the study data will be conducted when the last subject completes the Day 365 visit of the RCP or discontinues the RCP. The study will be complete when the last active subject completes all protocol-specified visits.

7 STUDY INTERVENTIONS

7.1 Description of Investigational Products

Table 7 provides a description of the IPs to be used in the study.

Investigational Product	Concentration and Formulation as Supplied	Route Dose	RCP Dosing Regimen	Manufacturer
Inebilizumab (100 mg per vial, nominal)	Inebilizumab for IV administration is supplied as a sterile liquid filled at a nominal volume of 10 mL in 10R vials. Each vial contains inebilizumab formulated at 10 mg/mL, in 20 mM histidine/histidine hydrochloride, 70 mM NaCl, 106 mM (4% [w/v]) trehalose dihydrate, and 0.01% (w/v) polysorbate 80, pH 6.0	IV 300 mg	Day 1, Day 15, and Week 26	AstraZeneca Nijmegen, B.V. (formerly MedImmune Pharma, BV)
Placebo	Placebo for IV administration is supplied in 10R vials filled with 10 mL (nominal) solution containing 10 mM histidine/histidine hydrochloride, 75 mM NaCl, 106 mM (4% [w/v]) trehalose dihydrate, and 0.02% (w/v) polysorbate 80, pH 6.0	IV	Day 1, Day 15, and Week 26	AstraZeneca Nijmegen, B.V. (formerly MedImmune Pharma, BV)

Table 7Description of Investigational Products and RCP Dosing

Table 7Description of Investigational Products and RCP Dosing

Investigational Product	Concentration and Formulation as Supplied	Route Dose	RCP Dosing Regimen	Manufacturer
				Berkshire Sterile Manufacturing, Inc.

IV = intravenous; NaCl = sodium chloride; RCP = randomized-controlled period; w/v = weight/volume.

7.1.1 Inebilizumab or Matched Placebo

7.1.1.1 Investigational Product Inspection

Each vial selected for dose preparation should be inspected. Both inebilizumab and placebo are supplied as a clear to slightly opalescent, colorless to slightly yellow solution, free from or practically free from visible particles. Inebilizumab is a sterile liquid drug product (100 mg inebilizumab per vial, nominal) intended for IV infusion following dilution in normal saline. Placebo is a sterile liquid product intended for IV infusion following dilution in normal saline.

Any defects with the IP must be reported immediately to the Sponsor's Quality Assurance Department and the site monitor. The Sponsor's Quality Assurance contact information for reporting product complaints is: [contact]. During the investigation of the product complaint, all IP must be stored at labeled conditions unless otherwise instructed.

7.1.1.2 Investigational Product Storage

Investigational product to be diluted for IV use will be appropriately labeled in accordance with national laws and regulations, including required translations. Investigational product is provided as 3 vials per blinded kit.

This IP should not be shaken and requires no special biohazard handling. It must be stored at 2°C to 8°C (36°F to 46°F) in a refrigerator with adequate temperature monitoring. The IP must not be frozen. It should be stored in the original outer package in a location with limited access.

7.1.1.3 Investigational Product Dose Preparation

Inebilizumab for IV administration and placebo for IV administration are supplied as a sterile liquid in a 10R glass vial at a nominal fill volume of 10 mL with 20-mm stopper and flip-off cap overseal.

No incompatibility has been observed between inebilizumab or placebo and IV infusion bags made of polyolefin or polyvinyl chloride. Inebilizumab and placebo do not contain preservatives and any unused portions must be discarded. Preparation of IP and IV bags is to be performed aseptically.

To prepare each inebilizumab or placebo dose, 3 vials of IP, one 250 mL IV bag containing 0.9% (weight/volume) saline, and one IV infusion pump are required. Each vial should be used only one time to prepare a single dose. With approval of the Sponsor (and using additional

administration instructions), 100 mL or 500 mL saline bags may be used if 250 mL bags are not available or not appropriate.

The dose preparation steps are as follows:

- The tab portion of the vial cap should be removed and the rubber stopper cleaned with 70% ethyl alcohol or equivalent.
- For each dose, 30 mL of blinded IP will be obtained from 3 vials by withdrawing 10 mL from each vial. Use a new needle for each withdrawal.
- Add 30 mL of blinded IP to the saline bag using aseptic technique.
- Gently mix the contents of the IV bag by inversion. Do not shake the solution. The saline bag should then be inspected to ensure the solution is clear.

Total in-use storage time from needle puncture of the IP vials to start of administration should not exceed 4 hours at room temperature or 24 hours at 2°C to 8°C (36°F to 46°F). Although prepared IP is stable for 24 hours at 2°C to 8°C (36°F to 46°F), the dose of IP must be mixed on the day of administration.

The prepared infusion solution should be at room temperature prior to the start of the IV infusion.

7.1.1.4 Investigational Product Dosing and Administration

Prior to each infusion in the RCP and OLP, the Investigator or other qualified medical personnel must confirm that none of the conditions requiring delay or discontinuation of IP administration are met (Section 6.4.1).

Premedication (from commercial supplies) with a corticosteroid (eg, methylprednisolone 100 mg IV or equivalent), an antihistamine (eg, diphenhydramine 25-50 mg orally or equivalent), and an anti-pyretic (eg, acetaminophen 500-650 mg orally or equivalent) will be administered approximately 30-60 minutes prior to each IP infusion.

Vital signs will be obtained prior to the start of each IP infusion. An experienced and qualified staff member will place the IV access.

The prepared solution will be administered IV via an infusion pump at an incrementally increasing rate through an IV line containing a sterile, low-protein binding 0.2 or 0.22 micron in-line filter according to the schedule in Table 8.

Table 8Infusion Rate for Investigational Product after Dilution in a 250 mL IV
Bag

Elapsed Time (minutes)	Infusion Rate (mL/hour)
0-30	42
31-60	125
61 to end of infusion	333

IV = intravenous.

Clinical Study Protocol	Horizon Therapeutics Ireland DAC
VIB0551.P3.S2 - MITIGATE	Inebilizumab
Amendment 9.1, 08AUG2023	IgG4-Related Disease

Unless an infusion reaction occurs resulting in discontinuation of infusion, the entire infusion bag contents must be administered and the tubing must be flushed with a volume of saline at least as large as that of the tubing to ensure complete delivery of the IP infused at a rate not to exceed 333 mL/hour.

After completion of the infusion, subjects will be observed for at least one hour.

Medically qualified personnel must be immediately available to respond to emergencies during administration of IP. Appropriate drugs and medical equipment to treat acute hypotensive, bronchoconstrictive, or anaphylactic reactions must be immediately available, and study personnel must be trained to recognize and treat these reactions. Additionally, appropriate drugs and medical equipment to treat IRRs must be immediately available, and study personnel must be trained to recognize and treat these reactions.

If an infusion reaction occurs, the site may stop or slow the infusion. Resumption of the infusion is at the discretion of the site. Management of infusion reactions will depend on the type and severity of the reaction and is at the discretion of the Investigator. For life-threatening infusion reactions, IP should be immediately and permanently stopped and appropriate supportive treatment administered. For less severe infusion reactions, management may involve temporarily stopping the infusion, reducing the infusion rate, and/or administering symptomatic treatment.

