6.2.3 Schedule of OLP Assessments and Procedures

6.2.3.1 Eligibility for OLP

Subjects eligible for the OLP must:

- 1. Have completed the RCP Week 52 visit (end of RCP).
- 2. Must not have had IP discontinued for any of the following safety reasons:
 - Anaphylaxis or a serious hypersensitivity reaction that occurred within 7 days after IV dosing and cannot be attributed to another known allergen exposure (see Appendix B).
 - Any adverse event (AE) or significant laboratory abnormality that, in the opinion of the Investigator, Sponsor, or SDMC, warrants discontinuation of dosing.
 - Any life-threatening (Grade 4) infection.
 - Any event of sepsis or febrile neutropenia.
 - Any infection listed as either a definite or probable opportunistic infection in Appendix A.
 - Any Grade 3 IRR.
 - Any Grade 4 serious adverse event (SAE).
 - Pregnancy or a decision to become pregnant.
 - Malignancy.
 - Absolute neutrophil count < 800 cells/ μ L confirmed by repeat testing.
 - Determination that the subject was ineligible for study participation and continuation of IP could pose a safety risk to the subject in the judgment of the Investigator or Sponsor.
 - Significant noncompliance with the study protocol, as judged by the Investigator or Sponsor.
 - Receipt of any B cell-depleting therapy (eg, rituximab, ocrelizumab, obinutuzumab, ofatumumab, commercially available inebilizumab).
- 3. Have completed a 28-day washout period after discontinuation of non-B cell-depleting, non-GC immunosuppressive therapy initiated during the RCP, if relevant.
- 4. Receive Dose 1 in the OLP within the window of 1-38 days after the RCP Week 52 visit (the final visit for the RCP and the first visit for the OLP cannot occur on the same day).
- 5. Have a planned taper of GCs to discontinuation by 8 weeks after OLP Dose 1, if receiving GC at the time of OLP entry.

To maintain the every-6-month dosing of IP, subjects should enroll in the OLP and be dosed as soon as is feasible after completion of the RCP. All SAEs and AEs that occur between the end of the RCP and start of the OLP must be collected at OLP Visit 1. Investigational product discontinuation rules apply during the OLP (Section 6.4.1).

Table 5 summarizes the schedule of procedures for the OLP.

Study Period					Open-Lal	oel Perio	d						
OLP Visit Number	OLP V1	OLP V2	OLP V3, V4	OLP V5	OLP V6, V7	OLP V8	OLP V9, V10	OLP V11	OLP V12, V13	OLP V14	OLP V15, 17, 19, 21	OLP V16, 18, 20,	OLP V22/EDV

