6.4 Discontinuation of Investigational Product, Withdrawal from Study, and Loss to Follow-up

6.4.1 Discontinuation of Investigational Product

IP must be discontinued if the Investigator determines that continuing it would result in a significant safety risk for that subject. The following events require discontinuation of IP:

- 1. Anaphylaxis or a serious hypersensitivity reaction that occurred within 7 days after IV dosing and cannot be attributed to another known allergen exposure (see Appendix B).
- 2. Any AE or significant laboratory abnormality that, in the opinion of the Investigator, Sponsor, or SDMC, warrants discontinuation of dosing.
- 3. Any AE of immune complex disease.
- 4. Any life-threatening (Grade 4) AE.
- 5. Any event of sepsis or febrile neutropenia.
- 6. Any infection listed as either a definite or probable opportunistic infection in Appendix A.
- 7. Any Grade 3 AE with the following exceptions:
 - A Grade 3 AE of flare or exacerbation of IgG4-RD (per protocol, these events are not reported as SAEs as they may represent the primary endpoint of the study)
 - A Grade 3 event that is not an IRR or infection, does not meet any other discontinuation criterion, and for which the SDMC has agreed that IP dosing can continue
- 8. Pregnancy or a decision to become pregnant.
- 9. Malignancy.
- 10. Absolute neutrophil count < 800 cells/µL confirmed by repeat testing.
- 11. Withdrawal of consent for further study participation or for further receipt of IP.
- 12. Receipt of prohibited medication(s) (see Section 7.5.1).
- 13. Determination that the subject was ineligible for study participation and continuation of IP could pose a safety risk to the subject in the judgment of the Investigator or Sponsor.
- 14. Significant noncompliance with the study protocol, as judged by the Investigator or Sponsor.

Severity of AEs will be graded according to the National Cancer Institute Common Terminology Criteria for Adverse Events (CTCAE) (Section 8.1)

Subjects with Grade 3 SAEs should have their AE data reviewed by the Investigator to specifically address whether or not IP should be discontinued or delayed to ensure patient safety, particularly for Grade 3 SAEs of infection (Section 7.1.1.4). The medical monitor(s) and the SDMC are available for discussions regarding suitability of repeat dosing in a subject who has had a Grade 3 SAE.
Clinical Study Protocol	Horizon Therapeutics Ireland DAC
VIB0551.P3.S2 - MITIGATE	Inebilizumab

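### Protocol Section 7.1.1.4 lets a site restart an infusion after a Grade 3 infusion-related reaction, although Section 6.4.1 requires IP to be discontinued

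*Protocol*

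**What the plan says.** Section 7.1.1.4 of the protocol allows the site to stop or slow the infusion when a reaction occurs, and adds that "Resumption of the infusion is at the discretion of the site". It makes management depend on the type and severity of the reaction and then gives two tiers:

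- Upper tier: "For life-threatening infusion reactions, IP should be immediately and permanently stopped and appropriate supportive treatment administered".
- Lower tier: "For less severe infusion reactions, management may involve temporarily stopping the infusion, reducing the infusion rate, and/or administering symptomatic treatment".

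Section 6.4.1 lists the events that require IP discontinuation. It opens with a general clause, "IP must be discontinued if the Investigator determines that continuing it would result in a significant safety risk for that subject". Three items matter here:

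- Item 1: "Anaphylaxis or a serious hypersensitivity reaction that occurred within 7 days after IV dosing and cannot be attributed to another known allergen exposure".
- Item 4: "Any life-threatening (Grade 4) AE".
- Item 7: any Grade 3 AE, with two exceptions. The first is an IgG4-RD flare or exacerbation. The second requires SDMC agreement and is confined to "A Grade 3 event that is not an IRR or infection, does not meet any other discontinuation criterion".

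Section 6.2.3.1 names "Any Grade 3 IRR" among the safety reasons for IP discontinuation that bar entry to the OLP.

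Section 7.1.1.4 begins with a check, made before each RCP and OLP infusion, that no Section 6.4.1 condition is present. Its paragraph on infusion reactions does not refer to Section 6.4.1.

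**The concern.** The two sections give different answers for one situation: a Grade 3 IRR while IP is running. Under Section 6.4.1 the subject has met a mandatory discontinuation criterion that the SDMC cannot waive. Under Section 7.1.1.4 the same reaction is below life-threatening, so a pause is acceptable and restarting is for the site to decide.

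Section 7.1.1.4 is the text staff would have in hand at that moment. A site that followed it literally could give the rest of the bag to a patient who had just had a severe reaction, and would breach Section 6.4.1 in doing so. IRR is an AESI in this trial (Section 8.4), and Section 2.1.4 reports rare serious infusion reactions with inebilizumab. The stake is patient safety and protocol compliance; no endpoint, alpha or power calculation is involved.

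**Working it through.** **The rules by grade.** Item 4 of Section 6.4.1 equates life-threatening with Grade 4, so a Grade 3 IRR falls in the lower tier of Section 7.1.1.4.

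| IRR grade | Section 7.1.1.4, during the infusion | Section 6.4.1 | Consistent? |
|---|---|---|---|
| 4 | Permanent stop | Discontinue (item 4) | Yes |
| 3 | Pause or slow; restart left to the site | Discontinue (item 7); neither exception applies | No |
| 1–2 | Pause or slow; restart left to the site | No grade-based trigger | Yes |

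Item 1 gives a weaker second example. A serious hypersensitivity reaction with no other known allergen requires discontinuation, but the sections diverge only if the site judges the reaction not life-threatening.

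**How many Grade 3 IRRs to expect.** The plan gives no figure to reproduce. Section 2.1.5.3 reports that all IRRs in the Study 1155 RCP were Grade 1 or 2, so the Grade 3 count was zero. The group sizes follow from the percentages there:

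- Placebo: 2 subjects were 3.6%, which gives 56 (check: 6/56 = 10.7%).
- Inebilizumab: 230 − 56 = 174 (checks: 3/174 = 1.7%, 8/174 = 4.6%, 16/174 = 9.2%).

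With zero events in n, the one-sided 95% upper bound is 1 − 0.05^(1/n).

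- Per subject, n = 174: 1 − 0.05^(1/174) = 1.707%. For the 80 planned inebilizumab subjects, 80 × 1.707% = 1.37.
- Per infusion, n = 174 × 2 = 348, assuming every subject received both scheduled infusions: 1 − 0.05^(1/348) = 0.857%. This RCP schedules 80 × 3 = 240 inebilizumab infusions, so 240 × 0.857% = 2.06, assuming a constant, independent risk.

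The range is therefore 0 to about 1.4 on the first basis and 0 to about 2.1 on the second. The second may be too high for later infusions, because Section 2.1.5.3 says reactions were most common with the first.

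**What a restart could deliver.** Table 8 sets 42 mL/h for the first 30 minutes and 125 mL/h for the next 30.

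- Volume given by 30 minutes: 42 × 0.5 = 21 mL.
- Volume given by 60 minutes: 21 + 125 × 0.5 = 83.5 mL.

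The total volume is taken as 250 mL (the SAP's dose example in Section 3.4.3) or 280 mL (if the 30 mL of IP in Section 7.1.1.3 is added without removing saline). The dose remaining out of 300 mg is:

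- At 30 minutes: 300 × (1 − 21/250) = 274.8 mg, or 300 × (1 − 21/280) = 277.5 mg.
- At 60 minutes: 300 × (1 − 83.5/250) = 199.8 mg, or 300 × (1 − 83.5/280) = 210.5 mg.

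These doses are illustrative, since neither document says when reactions occur.

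**The case against.** The best defence is that nothing truly contradicts. Section 6.4.1 is mandatory and Section 7.1.1.4 is permissive, so a site satisfies both by not restarting, and general discretion is normally read within a protocol's mandatory limits. Section 7.1.1.4 does not say that only life-threatening reactions call for a permanent stop. Staff have just checked the Section 6.4.1 list before starting the bag, and the general safety-risk clause applies as well. Section 6.4.1 can also be read as governing the course of treatment, with Section 7.1.1.4 covering acute care before a final grade is known.

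Much of this stands. Read plainly, Section 6.4.1 already bars giving the rest of the bag, and the pre-infusion check blocks later doses. The instruction to give the whole bag does no harm, because it excepts reactions that end the infusion. The mismatch remains all the same. The check comes before an infusion and does not cover one in progress, the reaction paragraph carries no pointer or limit by grade, and resuming the infusion is itself giving more IP after a discontinuation event.

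Two supporting points are weaker than they look. The grade definitions in Section 8.1 are stated for events not listed in CTCAE, and the OLP list in Section 6.2.3.1 may be carried-over wording. Neither is needed, because items 4 and 7 of Section 6.4.1 carry the argument.

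It is also fair to say that the counts bound reactions in a different disease and say nothing about how often a site would restart.

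**Conclusion.** The concern holds as a minor inconsistency in safety wording. Section 7.1.1.4 reflects item 4 of Section 6.4.1 but not item 7, so as written its discretion extends to a reaction for which discontinuation is compulsory.

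The likely reach is small: somewhere between none and one or two Grade 3 IRRs among inebilizumab subjects in the RCP. That range assumes the planned 80 subjects, full dosing, and a risk that carries over from NMOSD. The number of restarts cannot be estimated, and no projection is made for the OLP. Confidence is high on the mismatch in wording but does not extend to how sites would behave. The IP Administration Manual is mentioned in Section 6.3.3.1 but is not available here, and it may already set restart criteria.

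**What to change.** Add one sentence to the reaction paragraph of Section 7.1.1.4: after any reaction meeting a Section 6.4.1 criterion, including any IRR of Grade 3 or higher, the infusion is permanently stopped and not resumed; the site's discretion to resume applies only to reactions that meet none of those criteria.

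Leave Section 6.4.1 as it is, since the summary of changes records that its list was revised on US FDA advice. Bring the IP Administration Manual into line. The cost is a wording change with no added visits, procedures or patients.

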7.1.1.5 Monitoring of Dose Administration

Vital signs (body temperature, blood pressure, pulse rate, and respiratory rate) must be obtained:

- Within 60 minutes prior to IP administration
- 15 (\pm 5) minutes after the start of the infusion and then every 30 (\pm 10) minutes until completion of infusion
- At the completion of infusion (+ 10 minutes)
- $60 (\pm 10)$ minutes after dosing (repeated as needed until stable)

7.1.2 Investigational Product Accountability

Study site staff will maintain a record of the IP doses received, dispensed, administered, and destroyed. All records will be maintained with controlled access. The Investigator will administer the IP only to subjects included in this study and according to the procedures established in this study protocol. Each administration of IP will be documented and transferred to the eCRF.

